9.2.1. Serious Adverse Events

An SAE is any AE from this study that results in one of the following outcomes:

- death
- initial or prolonged inpatient hospitalization
- a life-threatening experience (that is, immediate risk of dying)
- persistent or significant disability/incapacity
- congenital anomaly/birth defect
- important medical events that may not be immediately life-threatening or result in death or hospitalization but may jeopardize the patient or may require intervention to prevent one of the other outcomes listed in the definition above. Examples of such medical events include allergic bronchospasm requiring intensive treatment in an emergency room or at home, blood dyscrasias or convulsions that do not result in inpatient hospitalization, or the development of drug dependency or drug abuse.

All AEs occurring after signing the ICF are recorded in the eCRF and assessed for serious criteria. The SAE reporting to the sponsor begins after the patient has signed the ICF and has received investigational product. However, if an SAE occurs after signing the ICF, but prior to receiving investigational product, the SAE should be reported to the sponsor as per SAE reporting requirements and timelines (see Section 9.2) if it is considered reasonably possibly related to study procedure.

Study site personnel must alert Lilly or its designee of any SAE within 24 hours of investigator awareness of the event via a sponsor-approved method. If alerts are issued via telephone, they are to be immediately followed with official notification on study-specific SAE forms. This 24-hour notification requirement refers to the initial SAE information and all follow-up SAE information. Patients with a serious hepatic adverse event should have additional data collected using the eCRF.

Pregnancy (during maternal or paternal exposure to investigational product) does not meet the definition of an AE. However, to fulfill regulatory requirements any pregnancy should be reported following the SAE process to collect data on the outcome for both mother and fetus.

Investigators are not obligated to actively seek AEs or SAEs in subjects once they have discontinued and/or completed the study (the patient disposition CRF has been completed). However, if the investigator learns of any SAE, including a death, at any time after a subject has been discharged from the study, and he/she considers the event reasonably possibly related to the study treatment or study participation, the investigator must promptly notify Lilly.

9.2.1.1. Suspected Unexpected Serious Adverse Reactions

Suspected unexpected serious adverse reactions (SUSARs) are serious events that are not listed in the IB and that the investigator identifies as related to investigational product or procedure. United States 21 CFR 312.32 and European Union Clinical Trial Directive 2001/20/EC and the associated detailed guidances or national regulatory requirements in participating countries require the reporting of SUSARs. Lilly has procedures that will be followed for the identification, recording and expedited reporting of SUSARs that are consistent with global regulations and the associated detailed guidances.

9.2.2. Adverse Events of Special Interest

9.2.2.1. Hypoglycemia

Patients will collect information on episodes of hypoglycemia after signing ICF until the last study visit (Follow up Visit or Early Termination Visit). For that purpose, patients will be trained about signs and symptoms of hypoglycemia, how to treat hypoglycemia, and how to collect appropriate information for each episode of hypoglycemia in the study according to the Schedule of Activities. Site personnel will enter this information into the eCRF hypoglycemia page at each visit.

Investigators should use the following definitions and criteria when diagnosing and categorizing an episode considered to be related to hypoglycemia: (the PG values in this section refer to values determined by a laboratory or International Federation of Clinical Chemistry and Laboratory Medicine plasma-equivalent glucose meters and strips) (ADA 2017):

Glucose Alert Value (Level 1):

- **Documented symptomatic hypoglycemia** is defined as any time a patient feels that he or she is experiencing symptoms and/or signs associated with hypoglycemia, and has a PG level of ≤ 70 mg/dL (≤ 3.9 mmol/L).
- **Documented asymptomatic hypoglycemia** is defined as any event not accompanied by typical symptoms of hypoglycemia, but with a measured PG ≤ 70 mg/dL (≤ 3.9 mmol/L).
- **Documented unspecified hypoglycemia** is defined as any event with no information about symptoms of hypoglycemia available, but with a measured PG ≤ 70 mg/dL (≤ 3.9 mmol/L).

Clinically Significant Hypoglycemia (Level 2):

- **Documented symptomatic hypoglycemia** is defined as any time a patient feels that he/she is experiencing symptoms and/or signs associated with hypoglycemia, and has a PG level of < 54 mg/dL (< 3.0 mmol/L).
- **Documented asymptomatic hypoglycemia** is defined as any event not accompanied by typical symptoms of hypoglycemia, but with a measured PG < 54 mg/dL (< 3.0 mmol/L).
- **Documented unspecified hypoglycemia** is defined as any event with no information about symptoms of hypoglycemia available, but with a measured PG < 54 mg/dL.

(<3.0 mmol/L).

Severe hypoglycemia (Level 3):

- **Severe hypoglycemia** is defined as an episode with severe cognitive impairment requiring the assistance of another person to actively administer carbohydrate, glucagon, or other resuscitative actions. These episodes may be associated with sufficient neuroglycopenia to induce seizure or coma. Blood glucose measurements may not be available during such an event, but neurological recovery attributable to the restoration of BG to normal is considered sufficient evidence that the event was induced by a low BG concentration.

Other hypoglycemia categories:

- **Nocturnal hypoglycemia** is defined as any hypoglycemic event that occurs between bedtime and waking.

If a hypoglycemic event meets the criteria of severe, it needs to be recorded as serious on the AE eCRF and reported to Lilly as an SAE.

To avoid duplicate reporting, all consecutive BG values ≤ 70 mg/dL (3.9 mmol/L) occurring within a 1-hour period may be considered to be a single hypoglycemic event (Weinberg et al. 2010; Danne et al. 2013).

In each case of suspected or confirmed hypoglycemia, it is important that the event be properly categorized, the effect of the intervention be assessed, and the frequency of hypoglycemia be evaluated. The role of dietary changes and physical exercise (or any other contributing factor) in the development of an event should be established. The patient should receive additional education, if deemed appropriate. The dose of concomitant antihyperglycemic medications may need to be reduced as outlined in section 7.4.2.

9.2.2.2. Severe, Persistent Hyperglycemia

Severe, persistent hyperglycemia will be collected during the trial to assess the risk of extreme imbalance in glycemic control.

Investigators will be trained on the application of criteria for deciding when and how to intervene with patients who do not reach glycemic targets. An additional therapeutic intervention should be considered in patients who develop severe, persistent hyperglycemia after randomization at the discretion of investigator in accordance with American Diabetes Association/European Association for the Study of Diabetes guidance. Rescue medication will be prescribed as add-on to randomized treatment, and patients will continue to follow the protocol-specified visit schedule.

Add-on glycemic rescue therapy will be allowed for patients who meet prespecified criteria for severe, persistent hyperglycemia in section 7.7.2 and no intercurrent cause of the hyperglycemia could be identified (investigators should first confirm that the patient is fully compliant with the

assigned therapeutic regimen and that he or she does not have an acute condition causing severe hyperglycemia).

9.2.2.3. Pancreatitis

Acute pancreatitis is defined as an AE of interest in all trials with tirzepatide including this trial. Acute pancreatitis is an acute inflammatory process of the pancreas that may also involve peripancreatic tissues and/or remote organ systems (Banks and Freeman 2006). The diagnosis of acute pancreatitis requires 2 of the following 3 features:

- abdominal pain, characteristic of acute pancreatitis (generally located in the epigastrium and radiates to the back in approximately half the cases [Banks and Freeman 2006; Koizumi et al. 2006]; the pain is often associated with nausea and vomiting);
- serum amylase (total and/or pancreatic) and/or lipase $\geq 3 \times \text{ULN}$
- characteristic findings of acute pancreatitis on computed tomography (CT) scan or magnetic resonance imaging (MRI).

If acute pancreatitis is suspected, appropriate laboratory tests (including levels of pancreatic amylase and lipase) should be obtained via the central laboratory (and locally, if needed). Imaging studies, such as abdominal CT scan with or without contrast, MRI, or gallbladder ultrasound, should be performed. If laboratory values and/or abdominal imaging support the diagnosis of acute pancreatitis, the patient must discontinue therapy with investigational product(s) but will continue in the study on another glucose-lowering regimen. The most appropriate diabetes therapeutic regimen will be decided by the investigator, based on the patient's clinical status. A review of the patient's concomitant medications should be conducted to assess any potential causal relationship with pancreatitis.

Each case of AE of pancreatitis must be reported. If typical signs and/or symptoms of pancreatitis are present and confirmed by laboratory values (lipase or amylase [total and/or pancreatic]) and imaging studies, the event must be reported as an SAE. For a potential case that does not meet all of these criteria, it is up to the investigator to determine the seriousness of the case (AE or SAE) and the relatedness of the event to study drug(s).

Each patient will have measurements of p-amylase and lipase (assessed at the central laboratory) as shown on the Schedule of Activities (Section 2) to assess the effects of the investigational doses of tirzepatide on pancreatic enzyme levels. Serial measures of pancreatic enzymes have limited clinical value for predicting episodes of acute pancreatitis in asymptomatic patients (Nauck et al. 2017; Steinberg et al. 2017a; Steinberg et al. 2017b). Thus, further diagnostic follow-up of cases of asymptomatic pancreatic hyperenzymemia (lipase and/or pancreatic amylase $\geq 3 \times \text{ULN}$) is not mandated but may be performed based on the investigator's clinical judgment and assessment of the patient's overall clinical condition. Only cases of pancreatic hyperenzymemia that undergo additional diagnostic follow-up and/or are accompanied by symptoms suggestive of pancreatitis will be submitted for adjudication.

All suspected cases of acute or chronic pancreatitis will be adjudicated by an independent clinical endpoint committee (CEC). In addition, AEs of severe or serious abdominal pain of unknown etiology will also be submitted to the adjudication committee to assess for possible pancreatitis or other pancreatic disease. Relevant data from patients with acute or chronic pancreatitis and those with severe or serious abdominal pain will be entered into a specifically designed eCRF page by study site or Lilly staff. The adjudication committee representative will enter the results of adjudication in a corresponding eCRF page.

9.2.2.4. Thyroid Malignancies and C-Cell Hyperplasia

Individuals with personal or family history of MTC and/or MEN-2 will be excluded from the study. The assessment of thyroid safety during the trial will include reporting of any case of thyroid malignancy including MTC and papillary carcinoma and measurements of calcitonin. This data will be captured in specific eCRFs. The purpose of calcitonin measurements is to assess the potential of tirzepatide to affect thyroid C-cell function, which may indicate development of C-cell hyperplasia and neoplasms. Tirzepatide should be discontinued (after first confirming the value) if post randomization calcitonin value is ≥ 35 ng/L (pg/mL) and has increased at least 50% over baseline. A consultation with a thyroid specialist (if not available, an endocrinologist) should be obtained.

If the increased calcitonin value (≥ 35 pg/mL and increases by $\geq 50\%$ compared to baseline) is observed in a patient who has administered a medication that is known to increase serum calcitonin, this medication should be stopped and calcitonin levels should be measured after an appropriate wash out period. If the confirmed calcitonin value is < 35 pg/mL, tirzepatide should be restarted when it is safe to do so.

9.2.2.5. Major Adverse Cardiovascular Events

Deaths and nonfatal CV AEs will be adjudicated by a committee of physicians external to Lilly with cardiology expertise. The nonfatal CV AEs to be adjudicated include:

- myocardial infarction
- hospitalization for unstable angina
- hospitalization for heart failure
- coronary interventions (such as coronary artery bypass graft or percutaneous coronary intervention)
- cerebrovascular events, including cerebrovascular accident (stroke) and transient ischemic attack

9.2.2.6. Supraventricular Arrhythmias and Cardiac Conduction Disorders

Treatment emergent cardiac conduction disorders will be further evaluated. Patients who develop any event from this group of disorders should undergo an ECG which should be submitted to the central reading center. Additional diagnostic tests to determine exact diagnosis should be performed, as needed. The specific diagnosis will be recorded as an AE. Events that meet criteria for serious conditions as described in Section 9.2.1 must be reported as SAEs.

9.2.2.7. Hypersensitivity Events

All allergic or hypersensitivity reactions will be reported by the investigator as either AEs or, if any serious criterion is met, as SAEs. Additional data, such as type of reaction and treatment received, will be collected on any AEs or SAEs that the investigator deems related to study drug(s) via a CRF created for this purpose. Additional samples should also be collected as outlined in Section 9.4.4. Study drug(s) should be temporarily interrupted in any individual suspected of having a severe or serious allergic reaction to study drug(s). Study drug(s) may be restarted when/if it is safe to do so, in the opinion of the investigator. If study drug(s) is permanently discontinued, the patient will receive another glucose-lowering treatment, judged by the investigator to be appropriate based on the patient's clinical status, and will continue in the trial to collect all planned efficacy and safety measurements.

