7.3. Blinding

This trial is an open-label study due to the differences in dosing schedule, titration, and devices between once-weekly tirzepatide and once-daily insulin glargine. It is not blinded between different doses of tirzepatide.

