6.13.2.8. Hypersensitivity Events

Hypersensitivity reactions and related information reported via the “Hypersensitivity and Anaphylactic Reactions” eCRF will be summarized by treatment. Two main analyses are performed:

- **Potential Immediate Hypersensitivity:** Analysis of TEAEs occurring from the start of study drug administration up to 24 hours after the end of study drug administration. For events without the hypersensitivity CRF, only date (no time) information is collected. Events occurring on the same date as the study drug injection date will be included.

- **Potential Non-Immediate Hypersensitivity:** Analysis of TEAEs occurring more than 24 hours after the end of study drug administration, but prior to subsequent study drug administration.

Summaries of all potential hypersensitivity reactions will be generated by PT with decreasing frequency by treatment. The AE database will be searched using predefined SMQs to identify events consistent with hypersensitivity events. Detailed searching criteria for hypersensitivity events can be found in [Appendix 1](#). Severe/serious hypersensitivity events identified by predefined SMQ searches will be considered AESIs.

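### The hypersensitivity eCRF follows the open-label investigator's causality opinion, so its by-treatment summary can show a difference due to attribution alone, and reactions with and without the form are timed by different rules

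*Protocol*

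**What the plan says.** Protocol 9.2.2.7 sets two levels of collection. The base level has no causality condition: "All allergic or hypersensitivity reactions will be reported by the investigator as either AEs or, if any serious criterion is met, as SAEs". The second level, with detail such as the type of reaction and the treatment given, "will be collected on any AEs or SAEs that the investigator deems related to study drug(s) via a CRF created for this purpose". Protocol 7.3 gives the blinding status of the person making that judgement: "This trial is an open-label study due to the differences in dosing schedule, titration, and devices".

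SAP 6.13.2.8 states that reactions reported on the hypersensitivity "eCRF will be summarized by treatment. Two main analyses are performed". The first of the two is potential immediate hypersensitivity: "Analysis of TEAEs occurring from the start of study drug administration up to 24 hours after the end of study drug administration". The second is potential non-immediate hypersensitivity: "Analysis of TEAEs occurring more than 24 hours after the end of study drug administration, but prior to subsequent study drug administration". For the immediate class the SAP adds: "For events without the hypersensitivity CRF, only date (no time) information is collected". It then gives the rule for those events: "Events occurring on the same date as the study drug injection date will be included".

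The same SAP section also searches the whole AE database with predefined SMQs and takes the severe or serious hits as AESIs. Neither step refers to relatedness.

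**The concern.** Incidence of allergic and hypersensitivity reactions is a listed safety endpoint (Protocol Table GPHO.2; SAP 4.4). A by-treatment table built from a form that is completed on the investigator's opinion of causality measures two things at once: how often reactions occur, and how readily an unblinded investigator blames the drug. An investigator may attribute a rash to a new weekly agent more readily than to a marketed insulin. If so, the table shows an excess on tirzepatide with no true difference behind it.

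The same opinion also decides how precisely an event is timed. A reaction judged related carries a clock time and is tested against 24 hours. A reaction judged unrelated carries a date and is tested against the injection date. Two identical reactions can then land in different rows.

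Cardiovascular events in this trial are adjudicated by a blinded committee (SAP 6.13.2.6). The protocol and SAP describe no comparable step for hypersensitivity.

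**Working it through.** The plan gives no figure to reproduce here. The check is a reading of the text plus two illustrations. All rates, relatedness shares and onset distributions below are assumptions, because the documents give none.

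**1. What depends on the causality opinion**

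- By-treatment summary of the form: yes. An event judged unrelated has no form.
- Membership of the immediate and non-immediate analyses: no. Both are defined on TEAEs, and events without the form are kept.
- Timing rule applied to an event: yes. The 24-hour window needs the form; without it the same-date rule applies.
- SMQ search, AESIs and overall incidence: no.

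**2. Size of the distortion in the form's summary**

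Expected events per arm on the form = n × true incidence × share judged related. With n = 239 per arm (Protocol 5.2) and an assumed true incidence of 3% in every arm, 239 × 0.03 = 7.2 reactions per arm.

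- Shares 60% (tirzepatide) and 20% (glargine): 7.2 × 0.6 = 4.3 against 7.2 × 0.2 = 1.4, ratio 3:1.
- Shares 40% and 30%: 0.40 / 0.30 = 1.3:1.
- Equal shares: 1:1.

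The ratio depends only on the shares, not on the incidence. As a second illustration, pool the three tirzepatide arms (3 × 239 = 717) against glargine (239), with true incidence 4% in all arms, and compute the probability that Fisher's exact test gives p ≤ 0.05:

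| Share judged related (tirzepatide / glargine) | Rates on the form | Ratio | Probability |
|---|---|---|---|
| 50% / 50% | 2.0% vs 2.0% | 1.0 | 0.036 |
| 60% / 40% | 2.4% vs 1.6% | 1.5 | 0.064 |
| 70% / 30% | 2.8% vs 1.2% | 2.33 | 0.215 |
| 90% / 30% | 3.6% vs 1.2% | 3.0 | 0.441 |

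Fisher's test is the SAP's default for categorical safety data (6.13). The pooling is for illustration only.

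**3. Size of the timing effect, weekly tirzepatide**

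Protocol 7.2.1.1 sets no time of day for the weekly injection. For an injection at clock hour T, an event within 24 hours falls on the next date if onset is later than 24 − T hours. The share of such events is:

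- uniform onset: T / 24;
- exponential onset with mean m hours, truncated at 24: [exp(−(24 − T)/m) − exp(−24/m)] / [1 − exp(−24/m)].

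| Injection | Mean 2 h | Mean 6 h | Mean 12 h | Uniform |
|---|---|---|---|---|
| 08:00 | about 0% | 5% | 15% | 33% |
| 12:00 | 0.2% | 12% | 27% | 50% |
| 20:00 | 13.5% | 50% | 67% | 83% |

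Example, 12:00 and mean 6 h: (exp(−2) − exp(−4)) / (1 − exp(−4)) = (0.135 − 0.018) / 0.982 = 0.12.

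These shares apply only to events without the form. Uniform onset gives the largest figure in each row.

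**4. The same effect, daily glargine**

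On schedule, every calendar day is an injection date. A reaction on the day after a dose still meets the same-date rule, so the share misplaced is close to zero. For the same reason almost no glargine event can be more than 24 hours after one dose and before the next. The non-immediate class is nearly empty in that arm however the form is completed.

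**The case against.** The strongest reply is that the listed endpoint is protected. Every reaction must be reported as an AE or SAE, the SMQ search covers the whole AE database, and the AESIs come from that search. This stands. A reader might infer that hypersensitivity incidence as a whole rests on unblinded opinion, or that reactions judged unrelated vanish from the immediate and non-immediate analyses. The documents support neither: both classes are defined on TEAEs, and the SAP provides for events without the form.

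A reader might also apply the next-date shares to all four arms. Daily dosing rules that out for glargine.

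A further reply is that the numbers are assumed. That also stands. The relatedness shares appear nowhere in the documents, the range includes no distortion, and the direction is assumed too. With early onset the timing effect is negligible for morning and midday injections.

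Finally, the form itself is not in the documents. Protocol 9.2.2.7 does not say that the form is used only for related events, and the SAP does not say where a date-only event on the day after a tirzepatide injection is placed. Restriction to related events is still the natural reading, and the SAP confirms that some events have no form. None of these replies explains why a table summarized by treatment should leave out reactions that an unblinded investigator judged unrelated.

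**Conclusion.** The concern holds in limited form. The by-treatment summary of the hypersensitivity eCRF depends on open-label causality opinion and can show a difference between arms that reflects attribution alone: 3:1, 1.3:1 or 1:1 under the three assumed pairs of relatedness shares.

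The timing split is affected less. Opinion determines which rule applies, not whether the event is counted. The exposure is mainly in tirzepatide events that occur within 24 hours but on the next date and have no form: for a 12:00 injection about 0.2%, 12% or 50% of within-24-hour events for mean onset 2 h, mean 6 h or uniform onset, and up to 83% at 20:00 if uniform.

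Overall incidence, the SMQ search and the AESIs are not affected. Separately, the immediate/non-immediate split is not comparable between weekly tirzepatide and daily glargine under any rule for the form.

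**What to change.** In Protocol 9.2.2.7, require the hypersensitivity eCRF for every AE or SAE reported as an allergic or hypersensitivity reaction, in all four arms, whatever the answer on relatedness. The form should record onset time and time of the last injection. The injection time has to be asked for: patients record date and time for each tirzepatide dose (Protocol 7.2.1.1), but for the first glargine dose only the date goes on the eCRF (Protocol 5.1). Keep relatedness as a recorded field. Nothing is lost, because Protocol 9.2 already asks for it on each AE.

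If the form cannot be changed, state in SAP 6.13.2.8 that comparison between arms rests on the SMQ search of the AE database and that the form's summary is descriptive only.

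In either case, do not compare the immediate/non-immediate split between tirzepatide and glargine. Do not apply a date-only rule to all events as a repair: it would keep nearly all glargine events in the immediate row while moving next-day tirzepatide events out of it.

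The cost is a few more eCRF pages for sites, or SAP wording alone for the second option. A residual limit remains: events found only by the SMQ search, and never reported by the investigator as hypersensitivity, would still have a date and no time.
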